**PROTOCOL TITLE: SMYLS: A Self-Management Program for Youth Living with Sickle Cell Disease**

**PRINCIPAL INVESTIGATOR: [name], RN**

## 1.0 Objectives / Specific Aims

### Primary Aims:

***Aim 1:** Assess feasibility of implementation processes among adolescents/caregivers, young adults, and providers including reach, enrollment, fidelity, adoption, acceptability, and satisfaction using the RE-AIM framework.*

***Aim 2:** Monitor health care activities that occur via adolescent/caregiver- or young adult-provider health communication and explore relationships between health care activities, such as provider screening, supporting, informing, and referring, and adolescent self-management behaviors, such as monitoring and tracking symptoms, attending clinic appointments, and administering home medications and treatments, and symptom outcomes.*

***Secondary Aim:** Obtain estimates of variability for measures of transition readiness, physical and psychological symptoms, healthcare utilization, and quality of life among adolescents, caregivers, and young adults.*

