### 3.0 Intervention to be studied

The web-based SMYLS app consists of three major components: patient-centered educational materials; symptom monitoring and tracking; and young adult (YA) and A/CG-provider communication. Educational materials on SCD pathophysiology, home management strategies, and symptom prevention are derived from patient-facing, guideline-based information endorsed by authoritative sources. Educational materials have been translated to an app-friendly format and are subdivided by age (up to 12 years, 12 – 17 years, adult), role (parent), or “hot” topics (hydroxyurea, research participation, hematopoietic stem cell transplantation). For symptom monitoring, pain is the predominant symptom YA and A/CG track via the app. YA and A/CG record pain scores and location via an avatar, then proceed through a series of screens to record

additional information pertaining to the pain, and additional symptoms that may co-occur. A graph is available by which YA and A/CG can observe trends in recorded pain, including specifics such as the numeric pain rating, the site of the pain, description of the pain, and actions taken to relieve pain. YA-provider or A/CG-provider communication is facilitated by a health history page intended for YA or A/CG to complete with their provider. In addition to this static option, the app also includes a link that takes the user to MyChart to complete a message to the provider via the EHR portal. Ideally, YA or A/CG will use the app daily to record and track symptoms, and as needed to access educational materials and message providers, and providers will communicate via messaging with YA or A/CG. However, a primary aim of this study is to assess participant engagement with the app. User activity and records are recorded in a secure database housed at TACHL for analysis.

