Data on young adult-provider or dyad-provider communication and healthcare activities will be collected via MyChart messaging. All messages between young adults and providers or dyads and providers will be retrieved as transcripts for analysis. Patients and families at the MUSC Pediatric Sickle Cell clinic do not frequently use MyChart messaging to communicate with providers and instead send text messages. To encourage use of the more secure EHR portal (MyChart) – which has the added benefit of improved provider workflow – participants will be compensated for sending messages via MyChart. Participants will be compensated with \$2 for each message with a maximum possible compensation of \$20. The number of messages sent will be tallied at the end-of-intervention (12 weeks) and provided in the form of a gift card at that time.

Data on self-management behaviors, including monitoring and tracking symptoms and administering home medications and treatments will be collected via the app and stored in the secure app database. Specifically, we will collect data on the frequency symptoms are recorded (pain, fatigue, fever, etc.) and the frequency of accessing the pain graph component of the app. We will also collect data via the app on medication adherence and recorded treatments for symptoms (drinking water, heating pad, etc.). Data on clinic appointment attendance, ED visits, and details of appointments to assess acceptability of the intervention will be obtained during weekly phone checks. Also during weekly phone checks, adolescent participants will be asked 2 – 3 questions on functioning from the PedsQL Sickle Cell Disease Module and young adult participants will be asked 2 – 3 questions on functioning from the Adult Sickle Cell Quality of Life Measurement Information System (ASCQ-Me).

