### **SECTION C. Procedures for Identifying, Reviewing and Reporting Adverse Events**

**1) Identifying.** Potential minimum risks identified for participants are outlined in the Protection of Human Subjects section of the K23 grant application and are also outlined in the IRB-approved protocol and informed consent document. Additional unknown risks may occur and, if so, will be identified through diligent monitoring by the PI, mentor, or PC throughout the conduct of this study. During the informed consent process, participants will be advised of the potential risks of participation as identified in the IRB-approved informed consent document and reminded throughout the study that the researchers should be promptly informed about any concerns regarding potential side effects, adverse events, or clinical deterioration. Participants will also be instructed to notify the PI, PC, and/or designee of any suspected adverse events immediately if possible. All participants will be recruited via the MUSC Pediatric Sickle Cell clinic and will be current patients of the clinic. Therefore, if a participant notifies the PI or PC of an acute medical event, the participant will be advised to follow the usual processes of care as directed by his/her regular provider at the Pediatric Sickle Cell clinic. This may include calling the Pediatric Sickle Cell clinic during regular hours, calling the on-call provider after hours, or going to the emergency department if recommended by the regular provider. Throughout the course of study enrollment, the researchers will maintain weekly telephone and/or face-to-face contact with the all study participants to elicit information about experienced AE and to monitor participant progress. The PI or PC will maintain an electronic record of all reported adverse events and notify the SMC of all reportable events as they occur. The SMC will have real-time access to the study database to review and monitor all reported SAE that were reported as related to the intervention. The PI (with the mentor) or PC will generate and provide de-identified monthly administrative human subject safety reports for the SMC to review participant progress, accrual and attrition rates, and monitor the frequency of all reported side effects and AE. Additionally, the BS will generate and provide de-identified cumulative administrative human participant semi-annual safety reports for the SMC to review.

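### Aim 2 concerns patient–provider communication in general, but only MyChart messages are coded, and contacts by text or phone are neither captured nor counted

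*Combined protocol and SAP*

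**What the plan says.** The Primary Aims word Aim 2 without reference to a channel: "Monitor health care activities that occur via adolescent/caregiver- or young adult-provider health communication and explore relationships between health care activities", with self-management behaviors and symptom outcomes on the other side of the relationship.

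Section 10.0 names one source. Data on "communication and healthcare activities will be collected via MyChart messaging", and the messages are retrieved as transcripts. The same section's list of measures mentions no other form of communication content. It then says that the clinic's families "do not frequently use MyChart messaging to communicate with providers and instead send text messages".

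The plan responds to this in three ways:
- Section 10.0 pays participants $2 per MyChart message, up to $20, tallied at 12 weeks.
- Section 3.0 states that "the app also includes a link that takes the user to MyChart to complete a message to the provider via the EHR portal".
- Section 10.0 makes MyChart communication the providers' study activity.

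Section C, item 1 of the safety monitoring plan covers a participant who tells the study team of an acute medical event. That participant is advised to follow usual care, which may include "calling the Pediatric Sickle Cell clinic during regular hours, calling the on-call provider after hours", or going to the emergency department.

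In Section 11.0, the transcripts are coded into activity categories and counted per family. The number and types of activities are then related to outcomes in adolescent/caregiver families. Separately, the number of adolescent/caregiver–provider messages is one of the app-use covariates in the repeated measures ANCOVA.

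**The concern.** The construct in Aim 2 is wider than the measurement. A family that keeps texting its provider is recorded as having little or no screening, informing, supporting or referring, however much actually took place. Nothing in the plan logs texts or calls to providers. The weekly phone checks ask about appointments, emergency visits and a few functioning items, and the safety sections add adverse events and progress.

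Three results inherit the gap: the activity counts, their relationships with outcomes, and the message covariate in the ANCOVA. In each, a low value can mean little communication or communication elsewhere. The payment adds a further influence, since some messages may be sent because they are paid for. On adoption, the study will have no count showing whether MyChart replaced texting or was added to it. That matters because Section F says the findings are to inform a larger efficacy trial.

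**Working it through.** The plan states no capture rate or channel share, so there is no figure of its own to reproduce. The check has four steps.

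**1. What the incentive covers.** $20 / $2 = 10 paid messages, or 10 / 12 = 0.83 per week over the 12-week intervention. If a family sent only those 10, the share captured would depend on its total contacts over 12 weeks, which is assumed here:

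| Assumed total contacts | Share captured |
|---|---|
| 12 | 10/12 = 83% |
| 20 | 10/20 = 50% |
| 24 | 10/24 = 42% |
| 36 | 10/36 = 28% |

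**2. How well recorded contacts track true contacts.** Let T be a family's true contacts, p its MyChart share and C the recorded contacts, binomial given T and p. If p is independent of T:

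- Var(C) = E[T²]E[p²] − (E[T]E[p])² + E[T]E[p(1−p)]
- Cov(C,T) = E[p]·Var(T)

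Assumptions: T is gamma-Poisson with shape 2 and mean 12 or 24. The share p is beta-distributed with mean 0.2 to 0.8 and concentration 2 (families differ widely) or 10 (families are more alike). With mean 12, Var(T) = 12 + 144/2 = 84 and E[T²] = 84 + 144 = 228.

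- *Low end*, mean share 0.2, concentration 2: Var(p) = 0.16/3 = 0.0533 and E[p²] = 0.0933. Var(C) = 228 × 0.0933 − 2.4² + 12 × 0.1067 = 16.8. Cov = 0.2 × 84 = 16.8. Correlation = 16.8 / √(84 × 16.8) = 0.447. A simulation of 400,000 draws gave 0.44.
- *High end*, mean share 0.8, concentration 10: Var(p) = 0.16/11 = 0.0145 and E[p²] = 0.6545. Var(C) = 228 × 0.6545 − 9.6² + 12 × 0.1455 = 58.8. Cov = 0.8 × 84 = 67.2. Correlation = 67.2 / √(84 × 58.8) = 0.96.

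Mean 24 gives the same ends to within rounding. The range is about 0.44 to 0.96.

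**3. What that does to an association.** If the share is also unrelated to the outcome given total contacts, an association is multiplied by this correlation. A true correlation of 0.40 would appear as about 0.18 (0.40 × 0.447) to 0.38 (0.40 × 0.96). In the same simulations, between 1% and 46% of families had no recorded contact. Few of those truly had none: the chance of T = 0 is (2/14)² = 2% at mean 12 and (2/26)² = 0.6% at mean 24.

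**4. When channel choice is not independent.** Step 3 then fails, and simple cases show both directions (shares assumed):

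- A sicker family has 24 contacts with a 25% MyChart share and is recorded with 24 × 0.25 = 6. A less sick family has 12 contacts with a 75% share and is recorded with 12 × 0.75 = 9. The order is reversed.
- Two families each have 12 contacts, with shares of 25% and 75%. They are recorded with 3 and 9. If the heavier portal user is also the more diligent symptom recorder, activity and self-management appear associated although contact was identical.

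**The case against.** The best case for the plan is that it saw the problem and acted on it. The statement about texting describes clinic practice without the study's incentive, so it does not predict behavior during the study. MyChart is also the messaging component of the intervention, so measuring it is reasonable. Aim 2 is exploratory, with no hypothesis test or decision rule. Adoption has further sources: Table 1 lists interviews and weekly quality checks, and Section F uses phone-call data on uptake and usability.

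Much of this stands. It rules out three stronger readings that a reader might infer:

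- *Most healthcare activity falls outside the data.* No channel share is given, and the incentive may work well.
- *Families are told to phone for acute events.* The advice applies when a participant notifies the study team, refers back to the family's own provider, and says only that it may include calling. This point does not question that advice.
- *Associations shrink by about 42% to 55%.* Those figures are correct arithmetic for one assumed case: total contacts with mean 12 and SD 6, and a mean share of 30% with SD 15% to 25%, giving correlations of 0.58 and 0.45. Other plausible shares give far less loss, and shrinkage itself requires the share to be unrelated to the outcome.

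What does not stand is that the mitigation closes the gap. Encouraging portal use does not count contacts made elsewhere, and without that count nobody can tell whether the encouragement worked. The interviews come after the intervention, with up to 15 of 30 dyads, up to 15 young adults and up to 5 providers. They can describe channel use but cannot supply a per-family count. Nor does the statement that all messages will be retrieved extend to texts: it directly follows the sentence on MyChart, and no procedure for obtaining texts is given.

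**Conclusion.** The concern holds as a gap in measurement coverage. Aim 2 is stated for communication in general, its only coded source is one channel, and the protocol itself says that families at this clinic usually use another. The activity counts and the message covariate partly reflect channel choice and response to payment.

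The size cannot be determined from the documents. Under assumed mean shares of 20% to 80%, independent of total contacts, the correlation between recorded and true contacts runs from about 0.44 to 0.96, so the loss could be serious or minor. If the share depends on illness or engagement, the direction of bias is unknown as well. The calculation concerns numbers of contacts. Aim 2 also analyzes types of content code, and one message can carry several, so the range is indicative only.

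Because the analyses are exploratory, this is a change that should be made, and not a flaw that invalidates the study.

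**What to change.** 1. In the existing weekly phone check, ask for the number of texts and the number of calls to clinic providers since the last check, for as long as MyChart messages are being collected.
2. Report MyChart's share of all counted contacts as an adoption measure.
3. Repeat the exploratory Aim 2 relationships as a sensitivity analysis that accounts for MyChart share or the total contact count. Do not assign activity codes to contacts that were not transcribed: a family's recollection of why it made contact does not identify what the provider did, and it is not comparable with coded transcripts.
4. State in Section 11.0 that conclusions about types of healthcare activity apply to MyChart communication.

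The cost is slightly longer weekly calls and some protocol wording. The counts rest on one-week recall, and the content of texts and calls stays unobserved. The acute-event advice is unaffected.

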##### *Inclusion Criteria:*

- Young Adults:
  - Age 18 – 25 years
  - Diagnosis of sickle cell disease, as reported by clinician at the MUSC Lifespan Sickle Cell Clinic
  - Self-reported history of pain (acute or chronic) at least once per month
  - Owns a smartphone
- Adolescents:
  - Age 11 - 17 years
  - Diagnosis of sickle cell disease, as reported by clinician at the MUSC Lifespan Sickle Cell Clinic

- Self-reported history of pain (acute or chronic) at least once per month
- Caregiver willingness to participate
- Owns a smartphone
- Caregivers:
  - The parent or primary caregiver of the adolescent
  - Owns a smartphone
- Healthcare Providers
  - At least 6 months' experience caring for individuals with SCD
  - Provides healthcare for adolescents with SCD

*Exclusion Criteria:*

- Adolescent or young adult not under the care of a provider participant
- Cognitive disability or delay that precludes ability to participate
  - Defined as: classified severe neurocognitive deficits as documented by neuropsychological evaluation in the medical record
- Lack of Wi-Fi access

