Reach: (primary aim) Sample Recruitment	Electronic log of sample characteristics; recruitment and enrollment activities	Recruitment tracking tools	Ongoing
Efficacy: Self-management outcomes (primary aim): Monitoring and tracking symptoms Attending clinic appointments Administering home medications and treatments Symptoms and health-related outcomes (secondary aim): Healthcare utilization (A only) Transition Readiness (A only) Pain (A only) Fatigue (A/CG) Depression (A/CG) Anxiety (A/CG) Sleep Interference (A/CG) Self-Efficacy (A/CG) Quality of Life (A/CG)	Pain and other symptom recording; treatments recorded; utilization reports 
 
PROMIS Pain Interference : Adult/Peds/parent proxy (8;0.87) (26)
 
PROMIS Fatigue SF : Adult (4; >0.9)(27); Peds/parent proxy (10 ; 0.87)(28)
 
PROMIS Emotional Distress: Depressive Symptoms SF : Adult (4; 0.97) (29); Peds/parent proxy (8; 0.94)(30)
 
PROMIS Emotional Distress: Anxiety SF Adult (4;0.97) (31); Peds/parent proxy (8; 0.83) (26)
 
PROMIS Self-Efficacy including general, manage daily activities, manage meds/treatment, manage symptoms: Adult (16; 0.97) (32)
 
Sickle Cell Self Efficacy Scale (9)
 
PROMIS Sleep Disturbance: Adult (4; 0.88)(33)
 
Adolescent Sleep Wake Scale (28; 0.86) (34)
 
Peds QL with Sickle Cell Disease Module (43; 0.95) (35)
 
Adult Sickle Cell Quality of Life Measurement Information System (30)
 
PROMIS Global Health Adult (10)
 
STARx (18; 0.8) (36)
 
Youth and Parent Sickle Cell Responsibility Scale
 
	YA, A/CG report Web-based application data capture Semi-structured interview Quality checks	Baseline, 6 weeks, 12 weeks, 3-months post intervention Ongoing Weekly
Adoption: (primary aim) Adherence (A/CG, HCP) Acceptability (A/CG, HCP) Education (A/CG) Symptom monitoring and tracking (A/CG) Communication (A/CG, HCP)	App overall use data; app component use data; satisfaction; reported problems; YA, A/CG-provider message content; MAUQ_SPA	Web-based application data capture Semi-structured interview Quality checks	Post intervention Ongoing Weekly

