## 11.0 Data Management

**Sex as a biological variable.** We recruit equal numbers of male and female adolescents and preliminarily explore for differences by sex in outcomes, such as acceptability, satisfaction, communication content, symptoms, quality of life, transition readiness, and utilization by conducting preliminary subgroup analyses in preparation for the subsequent larger trial.

**Feasibility processes.** Variables will include those pertaining to study procedures as well as participant variables. Specifically, 95% confidence intervals for proportions will be used to estimate dichotomous outcomes including the proportion of YA, A/CG who agree to participate out of the number approached, the proportion adherent to the intervention protocol, i.e., providing daily symptom monitoring/tracking, using the education component, responding to messaging, lost to follow up, etc. For the continuous feasibility measures (length of time spent in app components), frequency distributions and the median and mean responses with 95% confidence intervals will be obtained. Benchmarks for feasibility success are recruitment rate of at least 2 YA or A/CG per week, retention rates of 70%, use of at least one component of the app  $\geq 2$  days per week (adherence), and expressed satisfaction in key informant interviews (37).

**Outcome measures and estimates of variability.** Secondary aim outcomes variables will include measures of symptoms (pain, fatigue, depression, anxiety, sleep interference), quality of life, transition readiness, and utilization (number of appointments kept, number of ED visits). Demographic and clinical variables obtained at baseline will be described via measures of central tendency (mean, median), variability and frequency distributions as appropriate. Additionally, demographic and clinical characteristics for those who adhered to the study protocol versus those who did not adhere (non-adherers and drop outs) will be compared to better describe the study population. For continuous quality of life measures, the difference between pre-and post-intervention measurements will be estimated via 95% confidence intervals. To assess preliminary intervention effects, we will conduct repeated measures ANCOVA with variables in individual models adjusting for “dose” defined as number of times each portion of the app was accessed, total time spent in each portion of the app, number of days symptoms were recorded, and number of A/CG-provider messages.

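### Symptom-recording and symptom-treatment counts have no denominator, so these two self-management components, and the app dose built on one of them, can partly measure symptom burden

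*Combined protocol and SAP*

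**What the plan says.** Section 10.0 takes two self-management behaviours from the app. For monitoring, it states: "we will collect data on the frequency symptoms are recorded (pain, fatigue, fever, etc.) and the frequency of accessing the pain graph component". For home treatment, "We will also collect data via the app on medication adherence and recorded treatments for symptoms (drinking water, heating pad, etc". A third behaviour is collected by weekly phone check: "Data on clinic appointment attendance, ED visits, and details of appointments". The Efficacy row of Table 1 labels the self-management outcomes as primary aim and gives their measures as "Pain and other symptom recording; treatments recorded; utilization reports".

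Section 3.0 describes a diary entry that begins with a pain score and body location and then moves to "additional information pertaining to the pain, and additional symptoms that may co-occur". On frequency it says "Ideally, YA or A/CG will use the app daily to record and track symptoms". It does not describe an entry for a day without symptoms, and does not say that a score of zero is impossible.

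The inclusion criteria in section 5.0 require "Self-reported history of pain (acute or chronic) at least once per month", with no upper limit.

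Section 11.0 adjusts the repeated-measures ANCOVA for app dose, which includes "number of days symptoms were recorded, and number of A/CG-provider messages". The same section plans preliminary analyses relating healthcare activities, coded from messages, to self-management and symptom outcomes, as Aim 2 in section 1.0 foresees. Neither section gives a scoring rule, a denominator or an adjustment for symptom burden.

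**The concern.** A count of symptom events mixes two things: how many events there were, and how faithfully the participant recorded or treated them. Only the second is self-management. With eligible pain frequency running from about monthly to daily, the first can vary widely between participants, and it should fall within a participant if the intervention works.

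Three uses are exposed.
- **Describing behaviour.** The number of recorded treatments cannot be read as good or bad without knowing how many symptom days there were to treat.
- **Dose.** If recorded days follow symptom days, a covariate in the models for pain and other symptoms partly reflects the outcome it adjusts. A higher dose could then appear to go with worse symptoms.
- **Aim 2.** If participants with more symptoms also send more messages, healthcare activity could appear linked both to more self-management and to worse symptoms, with burden behind both. In a single-group study there is no comparison arm to expose this.

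**Working it through.** The plan gives no figure to reproduce, so this is a check of how the measures behave.

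**Inputs from the documents.** The intervention lasts 12 weeks, or 84 days (section 10.0). The entry floor is pain once a month (section 5.0), taken here as one pain day per 28 days. Every other input below is an assumption.

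**Treatment count with complete logging.**
- Participant A: 84/28 = 3 pain days, all treated and recorded, gives 3 treatment days.
- Participant B: two pain days a week, 2 × 12 = 24, half treated, gives 24 × 0.5 = 12.
- B treats a smaller share of pain days but has a count 12/3 = 4 times higher. As shares, A scores 3/3 = 100% and B scores 12/24 = 50%.

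Nothing here depends on missed entries, so daily logging does not cure it.

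**Recording count.** Let s be the share of days with symptoms, q the probability of logging a symptom day and f the probability of logging a symptom-free day. Expected logged days = 84 × [s × q + (1 − s) × f]. With equal diligence, q = 0.9:

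| f | s = 0.10 | s = 0.50 |
|---|---|---|
| 0 | 7.6 | 37.8 |
| 0.25 | 26.5 | 48.3 |
| 0.50 | 45.4 | 58.8 |
| 0.90 | 75.6 | 75.6 |

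A participant who improves from symptoms on 50% of days to 20%, with q fixed at 0.9 and f = 0, goes from 42 × 0.5 × 0.9 = 18.9 logged days in the first six weeks to 42 × 0.2 × 0.9 = 7.6 in the second. If f = q = 0.9, both halves give 42 × 0.9 = 37.8.

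**Correlations.** The simulation used 400,000 participants per scenario. Pain days were log-uniform from 3 up to 24 or 42 in 84 days. The probability of logging a pain day had mean 0.6 and SD 0.20, or mean 0.5 and SD 0.25, independent of pain. The ranges cover the four combinations.

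| Pain-free days logged, relative to pain days | Count with pain days | Count with true recording behaviour |
|---|---|---|
| never | 0.67–0.85 | 0.39–0.58 |
| one quarter as often | about 0.27–0.55 | 0.72–0.87 |
| half as often | 0.12–0.29 | 0.88–0.94 |
| equally often | 0.00 | 0.97–0.98 |

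**Messages.** If messages are assumed to arrive at 0.2 per pain day, the count correlates 0.43–0.66 with the number of messages when pain-free days are never logged, although behaviour and messaging were made unrelated. If messages do not depend on pain, the correlation is 0.00 throughout. Any Aim 2 effect therefore needs both conditions: under-recorded symptom-free days and messaging that rises with burden.

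**The case against.** The strongest reply is that the plan intends daily recording. Section 3.0 states it as the ideal and section 11.0 uses daily monitoring as an example of adherence. A pain score could be zero. If participants do log symptom-free days as reliably as symptom days, the recording count is a good measure of behaviour. That stands, and it makes this part of the point conditional. It does not close it: the daily ideal is only an ideal, the app-use benchmark in section 11.0 is two days a week on any component, and nothing says that a symptom-free entry is possible or counts. The reply does not reach the treatment count.

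Several stronger readings are tempting, and the documents do not support them.
- **That self-management as a whole is scored this way.** No composite is defined. Clinic attendance and medication adherence are also collected and need not rise with burden.
- **That the recording count has no direction.** Daily use is the ideal, so more recording is implicitly better. The ambiguity belongs to recorded treatments.
- **That well participants will be classed as poor self-managers.** No rule classifies anyone on these counts, and the two-day benchmark can be met through education or graph use.
- **That Aim 2 will show an association purely through burden.** The analyses are exploratory and no model is fixed. Payment of $2 per message up to $20 is an incentive to message that is unrelated to pain.

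Burden is also measured separately, for example by PROMIS Pain Interference at four time points, so conditioning on it is possible. The plan does not commit to doing so.

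**Conclusion.** The concern holds for two components and for the dose variable derived from one of them. For recorded treatments it holds however complete the logging, because the count scales with the number of symptom days. For symptom recording, and for recorded days used as dose, its size depends on how often symptom-free days are logged: from a correlation of 0.67–0.85 with pain days down to none. The documents do not say where the study will fall in that range, and the figures rest on assumed distributions of pain days and recording behaviour. For Aim 2 the conclusion is only that associations could partly reflect burden, provided that messaging rises with burden too.

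This is worth correcting before data collection because the measures serve a primary aim, and app counts alone cannot later separate a day without symptoms from a day not recorded.

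**What to change.** 1. State that a zero or no-symptoms-today entry counts as a record, and instruct participants to make one. Score monitoring as days with any entry over days observed. The denominator alone does not remove the dependence on burden; the symptom-free entries do.
2. Score home treatment as the share of recorded pain days (score above 0) with a treatment recorded. Show numerator and denominator, since a participant with three pain days can only score 0, 1/3, 2/3 or 1.
3. In the ANCOVA, use check-in days in place of symptom days as the app dose.
4. If the app cannot accept a zero entry, add one question on the number of pain days to the existing weekly call, and report recorded over reported pain days.

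The cost is protocol wording and participant instruction, plus either a brief entry on symptom-free days, which section 3.0 already treats as ideal use, or one extra question a week. The fallback in item 4 relies on a week's recall and, in the simulation, the share of pain days recorded correlated 0.76–0.86 with true behaviour, so it is second best to complete daily entries (0.97–0.98).
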